3. **Visual Analogue Scale for Anxiety (VAS-A).** The VAS-A is the primary measure of clinical symptoms of Acute Fear in both the R21 and R33. It has been used extensively as an indicator of acute fear symptoms. It is included because it provides a reliable indicator of rapid changes of affective state and is sensitive to the fear-inducing effects of 7.5% CO₂ in healthy volunteers. VASA consists of 11 items for 11 different symptoms (anxious, alert, fearful, relaxed, happy, feel like leaving, paralyzed, tense, nervous, irritable and worried) where for each item a mark is made on a 100 mm line scaled from 0 (not at all) to 100 (the most ever) to indicate symptom severity. The "Fearful" item will be used as the single primary endpoint due to its being consistently significantly increased in prior studies of CO₂ administration to healthy controls and evidence that anxiolytics can prevent 7.5% CO₂ mediated increases in this measure. The other 10 VAS-A items will be secondary outcomes. For each CO₂ administration ratings will be carried out at baseline (5 min prior to inhalation), and at 5, 10, 15, and 20 minutes into the inhalation and 15 minutes after inhalation ends. The peak effect will be obtained immediately after the end of the inhalation when the subjects will be asked to retrospectively rate the greatest intensity of effects experienced. A 26% increase in peak effect over baseline on the "fearful" item will be utilized as criteria for responding to CO₂ challenge as recommended based on prior work which suggests that approximately 50% of subjects will meet this criterion. The VAS-A "fearful" rating at 20 minutes from the start of CO₂ administration will serve as the primary outcome measure with the rating of peak effect being a key secondary outcome. The VAS-A may also be used during the anxiety task before, during, or after to measure changes in levels of subject anxiety from baseline to post-task administration.
4. **State Trait Anxiety Inventory (STAI).** The 20 item STAI will be included as a secondary clinical symptoms measure of state anxiety occurring with CO₂ administration. This was included because it has well-established psychometric properties and reflects changes in anxiety level with CO₂ administration in healthy controls and anxiolytic medication attenuated the CO₂ response with this measure. It consists of 20 items listing feelings and subjects rate their

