9.5 LIST THE DEVICES: List the medical devices or in vitro diagnostics to be studied or used. In the device details screen you will be asked questions such as:

- Whether the device is FDA approved or investigational
- Medicare device category
- If the device will be provided at no cost
- If an IDE is necessary, the IDE number, and who holds the IDE
- Risk category of the device
- FDA status of the device

Please see the [UCSF IRB website](#) for more details about the use of devices in research, including the [Investigator Checklist for Significant Risk, Non-Significant Risk, and/or IDE Exempt Device Studies](#) [Verification of IDE numbers: If the sponsor's protocol does not list the IDE number, you](#)

must submit documentation from the sponsor or FDA identifying the IDE number for this study. Attach this documentation in the Other Study Documents section of the Initial Review Submission Packet. If you have any correspondence from the FDA or sponsor regarding this device, please attach it to the application.

NeuroConn DC Stimulator MC-
No Yes 4

Manufacturer/Supplier of Device Rogue Resolutions

Medicare Category A B

Where will the Devices Be Stored Langley Porter Psychiatric Institute

Will Devices be supplied at no Cost Yes

Is this a HDE (HDE) No

HDE Number

Is the Device FDA Approved No

Is this a new device or a new use
of an already approved device Yes

Is an IDE necessary No

IDE Number

Who holds the IDE N/A

IDE Details

In the opinion of the sponsor,
select the level of risk associated
with this device No Significant Risk

9.6 * Is this an expanded access or compassionate use protocol, meaning the primary purpose is to diagnose, monitor or treat a patient's condition, rather than the collection of safety and efficacy data of the experimental agent: (REQUIRED)

Yes No

10.1 ENROLLMENT TARGET: How many people will you enroll:

If there are multiple participant groups, indicate how many people will be in each group:

Participants will be recruited in [name] laboratory at UCSF. We plan to enroll a total of 240 subjects healthy volunteers (age range: 21-65 years) in order to complete 100 for the entire effort (R21 and R33 Phases combined). This corresponds to enrolling 68 subjects in the R21 (34/year) and 172 (58/year) during the R33 phase. This takes into account the expected rate of failure to: have a pupillary response to the Auditory Oddball Test (25%) and CO₂ challenge

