- None of the above

10.7 INCLUSION CRITERIA: Briefly describe the population(s) that will be involved in this study. Include anyone that data will be collected from or about (e.g. patients, healthy controls, caregivers, providers, administrators, students, parents, family members, etc.):

Inclusion/Exclusion criteria were chosen to allow us to meet study aims and are comparable to those used in [name] prior study of transcranial alternating current (tACS) vestibular stimulation of healthy controls. Inclusion Criteria. 1) Age between 21-65; 2) Use of effective method of birth control for women of childbearing capacity; 3) Willing and able to provide informed consent; 4) Have a significant difference between the mean pupil diameter in response to rare vs common tones in the Auditory Oddball Test (AOT) or the Anxiety Task; 5) The 10 subjects in the R21 cross-over study and all of the R33 subjects must have a 26% increase in VAS-A "fearful" response to 7.5% CO₂ at the first CO₂ challenge session; 6) Able to follow study procedures.

10.8 EXCLUSION CRITERIA: List any exclusion criteria (e.g. reasons why someone would not be included in the study):

Exclusion Criteria. 1) Current or past Axis I DSM-IV disorder based on the MINI; 2) Current or past history of substance abuse or dependence (excluding nicotine) based on history or positive urine toxicology; 3) Current unstable medical condition; 4) Any current neurological condition or medical condition that is known to affect pupillary function, mood/anxiety, or neurologic function generally; 5) Pregnancy based on Urine Pregnancy Test; 6) Women who are breast feeding; 7) Use of medications known to affect CNS function within 5 half-lives screening; 8) Use of magnet controlled or programmed devices such as pacemakers, programmable ventriculoperitoneal shunts, or vagal nerve stimulators.

10.9 * RESEARCH CONDUCTED ON PATIENT CARE WARDS: Do any study activities take place on patient care units at UCSF medical facilities: (REQUIRED)

Yes No

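### The 26% CO₂ responder rule has no stated unit; read literally as a ratio to baseline it is undefined at zero and needs under 3 mm at low baselines

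*Combined protocol and SAP*

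**What the plan says.** Section 8.11, item 3, describes the VAS-A fearful item as a mark on a 100 mm line on which 0 means the feeling is absent and 100 is the most ever felt. Baseline is rated 5 minutes before CO₂ starts; section 8.9, item 8, has the subject breathing air through the mask at that time. The peak is rated after inhalation ends, when "the subjects will be asked to retrospectively rate the greatest intensity of effects experienced". A CO₂ responder is then someone with "A 26% increase in peak effect over baseline" on this item. The plan attributes the cut-off to prior work and expects about half of subjects to meet it.

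Section 10.7, inclusion criterion 5, turns this into an entry rule: the 10 cross-over subjects and "all of the R33 subjects must have a 26% increase in VAS-A" on the fearful item at the first CO₂ session. That criterion repeats the 26% but names neither the peak nor the baseline.

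Neither section gives a minimum rise in mm, a rule for a baseline of zero, or a statement that the percentage is of the full scale. The fearful rating at 20 minutes is also the primary outcome (8.11), and Hypothesis 3a in section 8.25 is judged by Cohen's d on it.

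**The concern.** An increase of 26% over baseline ordinarily means the change divided by the baseline value. On a scale with a true zero, that makes the hurdle proportional to how fearful the person already was, so the least fearful people face the easiest test. Section 10.8 excludes current or past Axis I disorder, so fearful ratings at or near zero before the gas starts are plausible.

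The purpose of the rule is enrichment: to randomise people in whom CO₂ produces enough fear for an effect of tDCS to be visible. If a trivial rise qualifies, some of those entered will have little fear to reduce, and the Cohen's d for Hypothesis 3a may be diluted by a floor. Separately, staff cannot apply the rule consistently if it can be read in two ways that give very different thresholds.

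**Working it through.** **Inputs from the documents:** 26% increase of peak over baseline, 0–100 mm line, about 50% expected to pass (8.11); 26% as an entry rule (10.7). **Not in the documents:** any mean, SD or distribution of baseline or peak fearful ratings.

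**The plan's own figure.** The 50% pass rate cannot be reproduced, because it needs the missing baseline and rise distributions.

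**Step 1. Rise required.** With baseline *b*, the ratio reading requires (peak − *b*)/*b* ≥ 0.26, so a rise of 0.26 × *b*. The scale-point reading requires 26 mm at every baseline.

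| Baseline (mm) | Ratio reading (mm) | Scale-point reading (mm) | 26 ÷ ratio-reading rise |
|---|---|---|---|
| 0 | undefined | 26 | – |
| 2 | 0.52 | 26 | 50 |
| 5 | 1.3 | 26 | 20 |
| 10 | 2.6 | 26 | 10 |
| 20 | 5.2 | 26 | 5 |
| 40 | 10.4 | 26 | 2.5 |

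At zero the percentage has no value. If the rule is rearranged as peak ≥ 1.26 × *b*, everyone with a zero baseline passes, including a person with no change.

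**Step 2. Limits.** The required rise is below 3 mm when *b* < 3/0.26 = 11.54 mm. The required peak exceeds the end of the line when *b* > 100/1.26 = 79.4 mm. Under the scale-point reading the corresponding ceiling is 100 − 26 = 74 mm.

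**Step 3. Illustration with no true CO₂ effect (assumed inputs).** Let the difference between the two ratings be normal with mean 0 and SD *s*. The chance of passing the ratio rule is 1 − Φ(0.26*b*/*s*). For *s* = 3, 5 and 10 mm:

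- *b* = 5 mm: 33%, 40%, 45%.
- *b* = 10 mm: 19%, 30%, 40%.
- A 26 mm rule, 1 − Φ(26/*s*): at most 0.5%, reached at *s* = 10.

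This ignores truncation at 0 and the fact that the peak is a recalled maximum. It shows direction only.

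**Step 4. Illustration with a true rise (assumed inputs).** If the rise has mean 20 mm and SD 20 mm, and *b* is 5 to 15 mm, the ratio rule passes 1 − Φ((0.26*b* − 20)/20), about 79–83%. A 26 mm rule passes 1 − Φ((26 − 20)/20) = 38%. Across four assumed rises (mean/SD 10/15, 20/20, 26/25 and 30/25 mm) at these baselines, the ratio rule passes 66–88% and the 26 mm rule 14–56%. The planned 50% lies in the second range, which hints at scale points. With every input assumed, it does not settle the reading.

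**The case against.** The best defence is that 26% on a 100 mm line is natural shorthand for 26 points. On that reading the zero-baseline and small-rise problems vanish. The cut-off is also said to come from prior work, with about half passing, so the only pass-rate evidence in the plan points away from a rule that nearly everyone meets. Baselines need not be near zero either: the rating is made minutes before the gas, with a mask on, and anticipatory fear is possible. All of this stands as a limit on the claim. It does not supply the missing unit, and the 50% applies here only if the rule is used in the units of that prior work, which the plan does not state.

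Three stronger readings are tempting, and the documents do not support them.

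- *Nearly everyone will pass, so the rule selects no one.* This needs low baselines and the ratio reading together; the first is not documented and the second is not certain.
- *The R33 comparison is biased.* A loose entry rule lowers sensitivity in both arms alike. By itself it does not favour either arm.
- *The enrolment target is wrong because its 50% CO₂ loss rests on this rule.* Sections 8.4 and 10.1 word that loss as failure to show a pupillary response to CO₂, not as failure of the VAS-A criterion. The matching 50% makes a link possible but does not establish it.

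The R21 cross-over also tests whether CO₂ raises the fearful rating (Hypothesis 1b, section 8.25). That is a check on the average rise in 10 people already chosen by this rule, so it does not check the cut-off.

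One caution remains. Section 8.4 describes a single CO₂ session in R33, after randomisation and with treatment in its last minutes, while 10.7 applies the rule at the first CO₂ session. A tighter cut-off would make the timing of that exclusion matter more. This is a separate question that restating the unit does not resolve.

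**Conclusion.** The point holds as a defect in the definition of an entry rule. Taken literally, the rule is undefined at 0, asks for under 3 mm at any baseline below 11.5 mm, and is unattainable above 79.4 mm. The alternative reading asks for 26 mm throughout, a 5- to 50-fold difference at baselines of 2–20 mm. These figures follow from the text alone.

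The consequence is conditional. If the ratio is meant and baselines are low, enrichment is weaker than intended and a floor on the primary endpoint could reduce sensitivity. Low baselines are plausible in this population but not shown, so the number of weak responders admitted is unknown. The change is worth making before R33 because the same item serves as both entry gate and primary endpoint.

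**What to change.** In 8.11 (item 3) and 10.7 (criterion 5), replace the ratio with one definition: retrospective peak fearful rating minus the pre-inhalation air baseline, at or above a stated number of mm on the 100 mm line. This covers zero baselines without a special rule.

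To set the number, confirm from the cited prior work whether its 26% was in scale points or relative to baseline. Then choose the mm cut-off that corresponds to the roughly 50% pass rate expected, and restate that rate if it changes.

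The cost is one line in each of two sections and a check of the source. Both ratings are already collected, so no new measurement is needed. If scale points were always intended, the change is pure clarification.

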This application responds to RFA-MH-15-300 (Exploratory Clinical Trials of Novel Interventions for Mental Disorders [R21/R33]) by proposing to translate neuroscience findings into a novel non-pharmacologic treatment for Acute Fear, a Research Domain Criteria (RDoC) construct common to many DSM defined anxiety disorders. The neuroscience findings which serve as the basis for this effort are an extensive preclinical body of work documenting that the region of the brainstem known as the locus coeruleus (LC) plays a key role in mediating symptoms of Acute Fear. We capitalize on evidence that LC activity can be non-invasively measured with pupillometry and our pilot data indicating that we can modulate LC activity with transcranial direct current stimulation (tDCS) applied via electrodes attached to the skin/scalp. Our approach is to develop tDCS as a means of inhibiting LC activity and then determine if this diminishes symptoms of Acute Fear.

Our translational effort will consist of two stages, a 2 year R21 phase where we establish feasibility, tolerability, safety, and proof-of-concept (POC) in terms of capacity to engage the neural target, followed by a 3 year R33 parallel-group, double blind, controlled trial. In the R21 phase we will employ an iterative approach where we use electric field modeling with a realistic head model to identify promising treatment electrode placements which we will test across a series of electrical doses in 3 cohorts of healthy controls to attempt to identify a tDCS treatment electrode configuration with which

we can identify a dosage in each subject that is: (1) tolerable (5-point Likert ratings of no more than mild discomfort); and (2) engages the target neural circuitry by transiently inhibiting LC activity as reflected in prevention of the pupil dilation response in the anxiety task or to rare stimuli in the auditory oddball task (AOT), tasks which reliably activate LC. If successful we will proceed to a 3 year R33 parallel group trial where 60 healthy volunteers are randomized to electrical dose-personalized active tDCS vs an active control therapy (tDCS that delivers the same skin current density as the active but does not affect LC) here clinical symptoms Acute Fear, the primary outcome, are elicited by inhalation of 7.5% CO₂. Future development viability will be assumed if there is preliminary evidence that engaging the target (inhibiting LC) safely diminishes clinical Acute Fear symptoms.

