It is important to note that the 4 mA maximum dosage is within recommended safety limits. We evaluated tDCS with: 1) the electrodes placed over the ears (external auditory meatus) and; 2) one electrode at the inion (notch on the back of the head at the top of the neck) and the other just under the chin. Pupillometry was carried out during the auditory oddball tasks (AOT) where two tones are played one more frequently than the other and the rare tones are well-established to lead to a neural response approximately 300 msec after the rare tones are played. We found that treatment was well-tolerated in general. We were able to find at least one electrode configuration and polarity (orientation of anode and cathode) associated with a tolerable stimulus intensity for all subjects that had a statistically significant effect on the pupillary AOT response. In 4/5 subjects there was an electrode configuration where the LC pupil dilation response to the rare stimuli was significantly suppressed by tDCS compared with both immediate pre and immediate post-stimulation testing (see Figure 3 for example). In 1 subject the response to the rare tones was enhanced by stimulation. In two of the subjects the direction of effect (suppression or enhancement) differed for the electrode configurations and polarities tested. These findings suggest that we can modulate LC function with tDCS with a substantial effect size, though the findings further indicate that electric field modeling will be needed to determine optimal treatment electrode placement given that effects appear to vary from person-to-person and that it is not possible to predict effects in a simple way, such that without modeling and iteration, we may be as likely to augment as inhibit LC activity, at least in some individuals. The findings also indicate that the effect size of inhibition is large enough to be statistically significant at the $p<0.05$ level in a single trial in an individual. These findings serve as a key basis for the proposed effort, support the need for work to determine optimal electrode placement before trials of tDCS for acute fear could be carried out, and support the use of the AOT as a target engagement measure.

8.7 * TREATMENT PROTOCOL: Is this a treatment study, i.e. does this study intend to provide treatment to individuals with a medical or psychological condition: (REQUIRED)

Yes No

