current state with respect to those feelings from 1 (not at all) to 4 (very much so). It will be administered just before and just after CO₂ administration.

5. **Generalized Anxiety Disorder-7 (GAD-7)**. The 7 item questionnaire may be administered at screening visits to identify anxiety state and trait correlations with pupil physiology.
6. **Beck Anxiety Inventory (BAI)**. This questionnaire may be administered at screening visits to identify anxiety state and trait correlations with pupil physiology.
7. **Adverse Effects (AE) Assessment**. The Systematic Assessment for Treatment Emergent Events (SAFTEE) will be used to monitor AEs. It is reliable and valid and used by [name] in prior studies.

Attach any unpublished instruments in the 'Other Study Documents' section of the Initial Review Submission Packet form after completing the study application. Published instruments should NOT be attached.

8.12 * BIOSPECIMEN COLLECTION: Are you drawing any blood or collecting other biosamples (e.g. tissue, buccal swabs, urine, saliva, hair, etc.): (REQUIRED)

Yes No

8.25 STATISTICAL METHODS: Briefly summarize the methods and types of analyses that will be performed:

All dependent measures will be tested for distribution normality and meeting homogeneity of variance requirements for parametric statistics. Data transformations will be conducted where indicated.

1. Primary Hypotheses.

R21. Testing R21 hypotheses equates to testing if the "Go-No-Go" criteria for proceeding to the R33 are met.

1) Hypothesis 2a: We can identify an electrode configuration for active tDCS that is well-tolerated (5-point Likert scale rating mild discomfort) and significantly suppress the Anxiety Task or Auditory Oddball

Task (AOT) pupil dilation response in 8/10 subjects in the 3rd round of treatment optimization. The Anxiety Task or AOT response will be determined using a repeated measures analysis of variance * (RMANOVA) with condition (common vs rare) as the independent measure and pupil diameter as the dependent repeated measure. If there is a statistically significant difference between the two conditions during treatment it will be assumed that suppression did not occur.

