11.0 Recruitment and Consent

11.1 * RECRUITMENT METHODS: What kinds of methods will be used to identify potential participants for recruitment (check all that apply): (REQUIRED)

- Medical records review
- Recruitment registry
- Re-contact of participants from the investigators' previous studies
- Referrals from colleagues (attach the 'Dear Colleague' letter or other recruitment materials you will provide to colleagues)
- Referrals from the community / word of mouth
- Advertisements (flyers, brochures, radio or t.v. ads, posting on clinical research sites or social media, presentation of the study at community events/media, etc.)
- Online recruiting tool such as TrialSpark
- CTSI Recruitment Services unit
- Other method (describe below)

Attach your recruitment materials (e.g., flyers, ads, recruitment letter templates, email text, etc.) in the Other Study Documents section of the Initial Review Submission Packet Form.

11.3 DETERMINATION OF ELIGIBILITY: How, when, and by whom will eligibility for recruitment be determined:

Flyers are placed around the UCSF campus and on the clinicaltrials.gov providing basic study information and eligibility criteria. Potential subjects will contact the study coordinator who will conduct a brief phone screen to determine initial eligibility criteria prior to scheduling the in-person screening visit. If the subject meets pre-screening criteria, an in-person screening visit will be scheduled at which time the subject will undergo screening procedures in [name] laboratory conducted by a study clinician. Normal healthy control subjects will be recruited and, following signing of informed consent, screened in the laboratory for whether they meet inclusion/exclusion criteria by [name] or other study clinician and a study coordinator trained by and working under the supervision of [name]. Assessments carried out during this visit will include a medical, psychiatric, and medication history, physical examination, urine drug screen, pregnancy test, and MINI. Those meeting entry criteria will then undergo the Anxiety Task or Auditory Oddball Task (AOT) administered by [name] or the study coordinator. Those with a statistically significantly greater pupil diameter response to the Anxiety Task or the cues for the rare vs common stimuli in the AOT will continue in the study and be scheduled for return visits.

Flyers will be placed around the UCSF campus and in non-investigator faculty offices.

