The study structure is such that there will be 4 cohorts of subjects each consisting of 10 subjects. Each of the first 3 cohorts will be stimulated with a different tDCS electrode configuration to determine if we can find one which is tolerable and inhibits locus coeruleus activity (as indicated by inhibition of a pupil dilatory response). After each cohort we will carry out an interim analysis to determine if this was the case (80% had tolerability ratings of 2 or less and there was statistically significant inhibition of the pupillary response to the anxiety task or auditory oddball task). Each of these interim analyses will be reported to the DSMB. If after the 3 cohorts are completed and if none of the 3 tDCS configurations tested meet the success criteria, then the study will cease. If one of the tDCS configurations meets the success criteria then an additional 10 subjects will be run using the successful tDCS configuration and using 7.5% CO2 instead of the anxiety task or auditory oddball test to elicit a pupillary response.

13.3 * DATA AND SAFETY MONITORING BOARD (DSMB): Will a Data and Safety Monitoring Board (DSMB) be established: (REQUIRED)

Yes

No

13.4 DSMB DETAILS: Provide details from the DSMB's charter, including meeting frequency, and affiliations and qualifications of members: If the DSMB has not yet been established, submit these details to us as they become available.

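### The R21 suppression rule ignores the sign of the rare-minus-common difference, so a significant reversal under tDCS would be scored as a failure to suppress (minor)

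*Combined protocol and SAP*

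**What the plan says.** Section 8.25, R21 Hypothesis 2a, sets the Go criterion as a well-tolerated configuration that suppresses the "pupil dilation response in 8/10 subjects in the 3rd round of treatment optimization". The response is tested by RMANOVA "with condition (common vs rare) as the independent measure and pupil diameter as the dependent repeated measure". The scoring sentence follows: "If there is a statistically significant difference between the two conditions during treatment it will be assumed that suppression did not occur". No direction is given, and a non-significant result is by implication suppression.

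Elsewhere the target has a direction:

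- The study summary describes "inhibiting LC activity as reflected in prevention of the pupil dilation response".
- The interim analysis plan in section 13.2 requires that "there was statistically significant inhibition of the pupillary response to the anxiety task or auditory oddball task".
- The pilot work in section 8.6 judged the response "significantly suppressed by tDCS compared with both immediate pre and immediate post-stimulation testing", and separated suppression from enhancement.

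For entry, inclusion criterion 4 (section 10.7) reads "Have a significant difference between the mean pupil diameter in response to rare vs common tones", without a sign. Section 11.3, which describes how screening is done, keeps "Those with a statistically significantly greater pupil diameter response", which has one.

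**The concern.** With two conditions the RMANOVA F statistic is the square of a t statistic, so significance alone does not show which response was larger. A rare response significantly above the common one is what the rule is meant to catch. A rare response significantly below it is not a preserved rare-stimulus dilation response, yet it gets the same label.

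The label matters in two places. It feeds the 8/10 count that helps decide whether the R33 phase goes ahead. It may also feed titration: section 8.4 has an unblinded team member compute the task response and tell the treating physician whether to continue or stop, and section 8.9 (item 2) ties continued participation to an effect on the response. The plan does not say that the section 8.25 rule drives those decisions. If it does, a reversed run would be reported as showing no suppression.

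**Working it through.** The plan gives no error rate or power for this rule, so there is no stated figure to reproduce.

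**Inputs**

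- Go criterion: at least 8 of 10 subjects (section 8.25).
- Significance level: not stated for this rule. Two-sided 0.05 is assumed, as in the pilot text of section 8.6; critical value 1.96.
- Power of one run to detect the undisturbed response: not stated. 75% is assumed, guided by the 25% screening failure rate in sections 8.4 and 10.1. That is a rate of people failing screening, not a per-run miss rate for enrolled responders, so it is a weak guide. Noncentrality = 1.96 + 0.674 = 2.63.
- One run per subject, subjects independent, unless stated otherwise.

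**Formulas.** Let f be the rare-minus-common difference under tDCS as a fraction of the undisturbed difference.

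- P(significant, rare < common) = Φ(-1.96 - 2.63f)
- P(significant, rare > common) = 1 - Φ(1.96 - 2.63f)
- The written rule fails a run on either event. A signed rule fails it on the second only.

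**Complete abolition (f = 0).** The written rule fails 0.025 + 0.025 = 5.0% of runs; the signed rule fails 2.5%. The chance of at least 8/10 is

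- written, p = 0.95: 0.0746 + 0.3151 + 0.5987 = 0.988
- signed, p = 0.975: 0.0230 + 0.1991 + 0.7763 = 0.998

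**Overshoot (f < 0)**

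| f | Φ(-1.96 - 2.63f) | Runs misread | P(≥8/10), written | P(≥8/10), signed |
|---|---|---|---|---|
| -0.25 | Φ(-1.30) | about 10% | 0.93 | about 1.00 |
| -0.50 | Φ(-0.64) | 26% | 0.49 | about 1.00 |
| -1.00 | Φ(0.67) | 75% | below 0.001 | about 1.00 |

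The last two columns assume that all ten subjects overshoot by the same fraction.

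**If more than one run may count.** Section 8.9 (item 3) gives 4-6 trials per visit, half with tDCS, so 2-3 tDCS runs. If a subject counts when either of two independent runs is scored as suppressed, the per-subject failure probability at f = -0.50 is 0.26² = 0.068 and P(≥8/10) rises from 0.49 to 0.97.

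**Cross-check without the 75% assumption.** A noncentral t calculation with 20 tones per condition (the Anxiety Task count in section 8.9), tones treated as independent, gives failure under the written rule in 33.8%, 69.3% and 86.9% of runs at standardized differences of -0.5, -0.8 and -1.0. Under the signed rule it is about 0 in each case. At +0.5 to +1.0 the two rules agree to three decimals per run, so the signed rule gives up nothing where dilation persists.

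**Entry.** For a person with no true response, the unsigned wording of section 10.7 admits 5%, half of them on a reversed difference; the signed wording of section 11.3 admits 2.5%.

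**The case against.** The strongest reply is that the rule works for the outcome it was written for. Abolition leaves no difference between conditions, and a non-significant result is scored as suppression. A reader might infer from the unsigned wording that abolishing dilation counts as failure; it does not, apart from the 5% false-positive rate. That part of the reply stands in full.

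Second, reversal is hypothetical. The pilot reports suppression in 4 of 5 subjects and enhancement in 1. Enhancement is a larger positive difference, which the rule scores correctly. No section reports a rare response below the common one. This also stands, and it means the overshoot rows above are scenarios, not forecasts. Titration by gradual increase makes a uniform overshoot in all ten subjects less plausible still.

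Third, a significant negative difference shows only that the common response exceeded the rare one; both may dilate. Section 8.9 (item 1) averages pupil diameter over a 0-12 s epoch and describes no baseline subtraction, and section 8.6 speaks of the separation between responses. On that view, treating any residual separation as not suppressed is conservative. It is arguable, but it sits poorly with a target stated as prevention or inhibition of dilation, and it gives opposite results one label.

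Fourth, a reader might take criterion 4 to have the same fault. Section 11.3 already applies it with the correct sign, so what remains is a mismatch of wording.

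**Conclusion.** The point holds in a narrow form and is minor. The section 8.25 rule is unsigned while the target is directional, so a significant reversal would be wrongly counted against the 8/10 criterion. When tDCS abolishes the response, the cost is small: 0.988 against 0.998 for reaching 8/10. For reversal, about 10% or 26% of runs would be misread at overshoots of -25% or -50%, given 75% power and a two-sided 5% level. The true frequency of reversal is unknown.

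A reader might infer that the rule roughly halves the chance of a Go decision, from the 0.49 figure. The documents do not support that: it needs every subject at -50% and a single run each, and becomes 0.97 if either of two independent runs may count.

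A larger weakness in the same sentence is separate and is not cured by adding a sign: a non-significant difference is taken as proof of suppression. At the 75% power assumed here, 25% of runs in which tDCS does nothing would be scored as suppressed under either rule.

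**What to change.** 1. In section 8.25, Hypothesis 2a, score a run as not suppressed only if the rare (or threat) response is significantly greater than the common (or safe) response during tDCS. Use the signed within-subject contrast in place of the F test, with its significance level stated. For the Anxiety Task, name the tone paired with stimulation as the threat condition, because section 8.9 allows it to be either the high or the low tone.
2. Report significant reversals as a separate category, and state in advance that they do not count as failures to suppress in the 8/10 tally.
3. Word inclusion criterion 4 in section 10.7 to match section 11.3.
4. Reconcile the titration text in sections 8.4 and 8.9 (item 2) with the signed score, and say whether that score is the one reported during titration.

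The cost is a few sentences and reading the sign of a contrast that is already computed; no new data are needed. Treating non-significance as suppression needs its own remedy. A directional within-subject test of the change in the rare-minus-common difference, tDCS against no tDCS or sham, would suit and would match sections 8.6 and 13.2.
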